10.5.2 Other secondary efficacy objectives

Unless otherwise stated the FAS will be used for the analysis of all other secondary efficacy endpoints. The exceptions are using the Molecular Responder Set for duration of MMR and time to MMR, the CCyR Analysis Set for CCyR rates, and the Cytogenetic Responder Set for duration of CCyR and time to CCyR.

No statistical testing of non-key secondary efficacy endpoints will be performed, and any analysis will be considered exploratory.

[figure not shown]
Molecular Response

MMR rates at scheduled time points (except 24 and 96 weeks which have been specified as primary and key secondary endpoints) will be evaluated in a similar fashion to the primary analysis of MMR rate at 24 weeks. Patients discontinuing the randomized treatment prior to a specific time point due to any reason will be considered as non-responders for that time point.

MMR rates by scheduled time points are defined as the proportion of patients who achieve MMR at or before the specified visit, i.e. if a patient achieves an MMR but then loses it before or at the visit, he/she will still be classed as achieving MMR by that time point.

For each endpoint the rate and the associated 95% confidence interval based on the Pearson-Clopper method will be presented by treatment group. Confidence intervals for the differences in any response rates between treatment groups will be provided using the Wald method.

Statistical testing will be performed via CMH chi-square tests stratified by the randomization strata. The Mantel-Haenszel estimate of the common risk difference and the corresponding 95% confidence interval will also be provided.

Duration of MMR is defined in [Section 7.2.1.1](#) as the time between the date of the first documented MMR and the earliest date of loss of MMR, progression to AP/BC, or CML-related death for patients in the Molecular Responder Set. The time will be censored at the last molecular assessment (PCR) date while on treatment for patients who have not experienced any of the above events.

Duration of MMR will be analyzed by K-M method and presented by K-M plots. The estimated rates of patients who are still responding at various time points will also be provided using K-M method.

The cumulative incidence of MMR will be graphically displayed by an increasing step function. This curve will increase each time (after randomization) at which a new responder is observed and thus will increase up to the best observed response rate (e.g. up to 50% if half of the patients in the analysis population are able to achieve response).

Time to MMR is defined in [Section 7.2.1.1](#) and calculated as: date of first MMR - date of randomization +1, for patients in the Molecular Responder Set. Descriptive statistics (minimum, maximum, median, quartiles, mean, sd) of time to MMR will be provided for the two treatment groups separately.

Cytogenetic Response

Patients in FAS will be categorized with counts and percentages provided for cytogenetic response (Complete, Partial, Major, Minor, Minimal, No Response) at and by (i.e. best response up to a specified time point) scheduled time points. Shift tables will also be employed to examine the changes in cytogenetic response category from baseline.

Since there are expected to be only limited numbers who are actually in CCyR at baseline the analysis of CCyR rate at and by scheduled time points will only include patients who are not in CCyR at baseline, i.e. the CCyR Analysis Set.

CCyR rates at and by scheduled time points etc. and the associated 95% confidence intervals based on the Pearson-Clopper method will be presented by treatment group with the analysis of these endpoints only including patients who are not in CCyR at baseline.

Confidence intervals for the differences in any response rates between treatment groups will be provided using the Wald method.

Statistical testing will be performed via CMH chi-square tests stratified by the randomization strata. The Mantel-Haenszel estimate of the common risk difference and the corresponding 95% confidence interval will also be provided.

Time to CCyR is defined for patients in the Cytogenetic Responder Set as: date of first CCyR - date of randomization +1. Descriptive statistics (minimum, maximum, median, quartiles, mean, sd) of time to CCyR will be provided for the two treatment groups separately.

The cumulative incidence of CCyR will also be graphically displayed by an increasing step function. This curve will increase each time (after randomization) at which a new responder is observed and thus will increase up to the best observed response rate.

Duration of CCyR is defined as the time between date of first documented CCyR and the earliest date of loss of CCyR, progression to AP/BC, or CML-related death for patients in the

Cytogenetic Responder Set. The time will be censored at the last cytogenetic assessment date on treatment for patients for whom none of the above events is reported or last PCR evaluation on treatment indicating MMR.

Duration of CCyR response will be analyzed by K-M method and presented by K-M plots. The estimated rates of patients who are still responding at various time points will also be provided using K-M method.

Treatment failure, disease progression and survival

Time to treatment failure (TTF) is defined as the time from date of randomization to an event of treatment failure. The following events will constitute ‘treatment failure’, and are based on the ELN criteria ([Baccarani et al 2013](#)) defining failure of a second line treatment adapted to include discontinuation of randomized treatment as an event:

- No CHR or > 95% Ph+ metaphases at three months after randomization or thereafter
- BCR-ABL1 ratio > 10% IS and/or > 65% Ph+ metaphases at six months after randomization or thereafter
- BCR-ABL1 ratio > 10% IS and/or > 35% Ph+ metaphases at 12 months after randomization or thereafter
- Loss of CHR, CCyR or PCyR at any time after randomization
- Detection of new BCR-ABL1 mutations which potentially cause resistance to study treatment at any time after randomization
- Confirmed loss of MMR
- New clonal chromosome abnormalities in Ph+ cells: CCA/Ph+: at any time after randomization
- Discontinuation from randomized treatment for any reason

[figure not shown]
For patients who have not reached treatment failure, their TTFs will be censored at the time of last study assessment (PCR, cytogenetic, hematologic or extramedullary) before the cut-off date.

Progression-Free-Survival (PFS) is defined as the time from the date of randomization to the earliest occurrence of documented disease progression to AP/BC or the date of death from any cause (including progressions and deaths observed during the survival follow-up period) before the cut-off date.

The time will be censored at the date of last study assessment (PCR, cytogenetic, hematologic or extramedullary) or last post-treatment follow-up for patients without event.

Overall survival (OS) is defined as the time from the date of randomization to the date of death (including the survival follow-up period). Patients who are alive at the time of the analysis data cutoff date will be censored at the date of last contact before the cut-off date.

TTF, PFS and OS will be estimated and graphically displayed using the K-M approach on FAS. The estimated rates by K-M method at various time points will be provided and the endpoints will be compared between the two treatment groups using stratified log-rank test stratified by the randomization strata. The hazard ratio and 95% confidence intervals will be computed from a stratified Cox model.

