Study treatment	Includes any drug or combination of drugs in any study arm administered to the patient (subject) as part of the required study procedures, including placebo and active drug run-ins. In specific examples, it is important to judge investigational treatment component relationship relative to a study treatment combination; study treatment in this case refers to the investigational and non-investigational treatments in combination.
Study treatment discontinuation	Point/time when patient permanently stops taking study treatment for any reason
Treatment group	A treatment group defines the dose and regimen or the combination, and may consist of 1 or more cohorts. Cohorts are not expanded, new cohorts are enrolled.
Variable	Identifier used in the data analysis; derived directly or indirectly from data collected using specified assessments at specified time points
Withdrawal of study consent	Withdrawal of consent from the study occurs only when a subject does not want to participate in the study any longer, and does not allow any further collection of personal data

[figure not shown]
Protocol summary:

Title	A phase 3, multi-center, open-label, randomized study of oral ABL001 (asciminib) versus bosutinib in patients with Chronic Myelogenous Leukemia in chronic phase (CML-CP), previously treated with 2 or more tyrosine kinase inhibitors
Brief title	Study of efficacy of CML-CP patients treated with asciminib versus bosutinib, previously treated with 2 or more TKIs
Sponsor and Clinical Phase	Novartis Phase 3
Investigation type	Drug
Study type	Interventional

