4.3 Definition of end of study

The patients are treated in the study up to end of study treatment period defined as up to 96 weeks after the last patient receives the first dose or up to 48 weeks after the last patient has switched to asciminib treatment whichever is longer unless patients have discontinued treatment earlier. The end of the study, concluding the survival follow-up, will occur 5 years from the date when the last patient enrolled into the study receives the first dose of the randomized treatment.

The primary analysis (cut-off date) is defined as the date when all randomized patients have been on study treatment for 24 weeks ([Section 10.4](#)) or discontinued earlier. Subsequent to this

analysis, the primary clinical study report (CSR) will be developed. Following the cut-off date for the primary CSR, the study will remain open. Patients who are ongoing at the time of the primary analysis will continue to receive the assigned study treatments (asciminib or bosutinib) during the study treatment period as defined above. The end of study treatment analysis will be conducted with a cut-off date 30 days after the end of study treatment period to ensure all available treatment data from all patients in the study is analyzed and summarized in a CSR.

After the end of the study treatment period the assigned study treatment will be made available to patients who in the opinion of the Investigators are still deriving clinical benefit. This may be outside of this study through alternative options including, but not limited to, an expanded access/compassionate use /managed access program or access to commercial supplies in applicable countries.

Patients will be followed for survival and progression for up to 5 years from the date the last randomized patient receives the first study dose (irrespective of treatment switch for patients failing bosutinib). Information on subsequent treatments will also be collected. An updated analysis of OS and PFS will be performed at the end of the follow-up period in the final study CSR.

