	20 mL	Week 8 / S-Week 8	Pre-dose
	20 mL	Week 12 / S-Week 12	Pre-dose
	20 mL	Week 16 / S-Week 16	Pre-dose
	20 mL	Week 24 / S-Week 24	Pre-dose
	20 mL	Week 36 / S-Week 36	Pre-dose
	20 mL	Week 48 / S-Week 48	Pre-dose
	20 mL	Week 60 / S-Week 60	Pre-dose
	20 mL	Week 72 / S-Week 72	Pre-dose
	20 mL	Week 84 / S-Week 84	Pre-dose
	20 mL	Week 96 / S-Week 96	Pre-dose
	20 mL	Every 12 weeks thereafter up to end of study treatment	Pre-dose
20 mL	End of Treatment / S-End of Treatment	Anytime	
Blood for BCR-ABL1 Mutation analysis by Sanger Sequencing	5 mL	Week 1 Day 1 /S-Week 1 Day 1*	Pre-dose
	No sample collected - testing is performed on the "Blood for BCR-ABL1 quantification by RQ-PCR" sample	Upon confirmed loss of MMR and/or End of Treatment/ S-End of Treatment	Anytime
Blood for BCR-ABL1 Mutation analysis only for patients with mutations at Week 1 Day 1	No sample collected - testing is performed on the "Blood for BCR-ABL1 quantification by RQ-PCR" sample	Week 12 and every 12 weeks thereafter up to end of study treatment	Anytime

*Assessment does not need to be completed during the visit for patients in the treatment switch if already collected during the EOT or the treatment switch screening visit.

During the study, peripheral blood samples will be collected into PAXgene™ Blood RNA tubes for all RQ-PCR assessments. Detailed instructions for the collection, handling, and shipment of RQ-PCR and mutation samples are outlined in the [\[CABL001A2301 Laboratory Manual\]](#).

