10.5 Secondary objectives

The secondary objectives in this study are as follows:

- To compare additional parameters of the efficacy of asciminib versus bosutinib, defined as:

Key secondary endpoints

[figure not shown]
- MMR rate at 96 weeks

Other efficacy endpoints

- Cytogenetic response (Complete, Partial, Major, Minor, Minimal, no response) rate at all scheduled data collection time points including, 24, 48 and 96 weeks.
- Cytogenetic response (Complete, Partial, Major, Minor, Minimal, no response) rate by all scheduled data collection time points including, 24, 48 and 96 weeks.
- MMR rate at all scheduled data collection time points (except 24 and 96 weeks which are already covered by primary and key secondary endpoints)
- MMR rate by all scheduled data collection time points including 24, 48 and 96 weeks.
- Time to MMR
- Duration of MMR
- Time to CCyR
- Duration of CCyR
- Time to treatment failure
- Progression free survival
- Overall survival
- To compare the safety and tolerability profile of asciminib versus bosutinib
- To characterize the PK of asciminib in the CML-CP population

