10.6.1.1 Data analysis of exploratory efficacy objectives

Subgroup analyses will be performed to evaluate the influence of factors such as baseline major cytogenetic response status, baseline/Week 1 Day 1 BCR-ABL1 ATP-binding site mutation status (from local historical record and from Sanger Sequencing), failure/intolerance to prior TKIs, line of therapy, gender, race and age on the primary efficacy endpoint. In addition, a logistic regression analysis will incorporate the key baseline variables into the model to further evaluate the impact of these variables on the primary endpoint and to provide a treatment effect estimate which is adjusted for imbalances in the treatment groups. An adjusted odds ratio for the treatment effect with associated 95% confidence intervals will be presented. Mantel-Haenszel estimates of the common odds ratio and the corresponding 95% confidence interval will also be provided. The effect of asciminib when administered as treatment after bosutinib failure will be assessed using the Switch Analysis Set to estimate response rates (cytogenetic and molecular response) at all scheduled time points after switch, as well as time-to and duration

of response. The analysis of time-to-event endpoints will be conducted only if at least 5 events are observed.

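### MMR rates at visits after Week 96 count patients whose treatment ended on plan as non-responders, so the rates and the arm difference fall with enrolment date

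*Combined protocol and SAP*

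**What the plan says.** - **Endpoint.** Section 10.5 lists as a secondary endpoint the "MMR rate at all scheduled data collection time points", leaving out Weeks 24 and 96 because they are the primary and key secondary endpoints.
- **Denominator.** Section 10.5.2: "Unless otherwise stated the FAS will be used for the analysis of all other secondary efficacy endpoints". The listed exceptions do not include the MMR rates.
- **Non-responder rule.** Section 10.5.2: "Patients discontinuing the randomized treatment prior to a specific time point due to any reason will be considered as non-responders for that time point". The same paragraph says these rates are evaluated in the manner of the primary analysis. Section 10.4.3 there accepts as responders only patients in MMR at the visit itself, and imputes a missing result only when evaluations on both sides of the visit show MMR.
- **PCR schedule.** Table 7-3 in section 7.2.1.1, after Week 96: "Every 12 weeks thereafter up to end of study treatment".
- **End of treatment.** Section 4.3 sets one end for the whole trial: "up to 96 weeks after the last patient receives the first dose or up to 48 weeks after the last patient has switched". The later of these two dates applies. Section 6.1.5 confirms that no fixed duration per patient is planned.
- **Discontinuation.** The glossary entry for study treatment discontinuation reads "Point/time when patient permanently stops taking study treatment for any reason". It makes no exception for reaching the planned end.

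**The concern.** With a common calendar end date, how far beyond Week 96 a patient can be assessed depends on when that patient enrolled. The denominator nevertheless stays at all randomised patients, and anyone without an on-treatment result at the visit is a non-responder. A late-visit rate therefore mixes response with enrolment date.

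Both arms lose patients to the planned end in about the same proportion, because enrolment date is independent of randomised arm. The two rates therefore shrink by a common factor, and so does their absolute difference. Section 10.5.2 prescribes confidence intervals and Mantel-Haenszel risk differences for these rates. Section 10.7 foresees an end-of-treatment analysis, if required, along the lines of the 96-week one. That report could show durable MMR by Kaplan-Meier beside MMR rates that appear to collapse.

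**Working it through.** **The plan's own figures.** The plan gives no number for this issue. Its sample size reproduces: 15% versus 35%, two-sided 5%, 90% power, 2:1, pooled variance without continuity correction gives 74 + 148 = 222, as in section 10.8. The Table 10-2 case of 30% versus 53% gives power 0.912 (stated as 90%). Those Week 96 rates are used below for illustration only.

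**Inputs.** The amendment rationales give 38 randomised by 29-Jun-2018, 86 by 21-Nov-2018, and 233 in total with recruitment completed on 22-Oct-2019.

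**Assumptions.**
- The last first dose falls on 22-Oct-2019.
- Accrual is linear between the stated dates.
- The true MMR rate is constant after Week 96 and unrelated to enrolment date.
- The 96-week limb sets the end of treatment.

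**Step 1, who can reach a visit.** A patient who starts t weeks before the last patient can be treated to Week 96 + t. Visit W therefore needs t ≥ W − 96. From 21-Nov-2018 to 22-Oct-2019 is 335 days = 47.9 weeks, and 233 − 86 = 147 patients entered in that time, or 147 / 47.9 = 3.07 per week. For t up to 47.9, the number able to reach the visit is 233 − 3.07t.

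- Week 108: 233 − 3.07 × 12 = 196
- Week 120: 233 − 3.07 × 24 = 159
- Week 132: 233 − 3.07 × 36 = 122
- Week 144: t = 48, almost exactly the 47.9 weeks back to 21-Nov-2018, so 86, nearly a direct reading

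**Step 2, the reported rate.** Reported rate = true rate × f, where f is the share able to reach the visit. Differences use unrounded shares.

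| Visit | Able to reach, of 233 | f | 53% and 30% reported as | 23-point difference reported as |
|---|---|---|---|---|
| Week 108 | 196 | 84.2% | 44.6% and 25.3% | 19.4 |
| Week 120 | 159 | 68.4% | 36.2% and 20.5% | 15.7 |
| Week 132 | 122 | 52.5% | 27.8% and 15.8% | 12.1 |
| Week 144 | 86 | 36.8% | 19.5% and 11.0% | 8.5 |

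With the denominator limited to patients who could reach the visit, every row would read 53% and 30%, difference 23.

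**Step 3, the other limb.** Section 7.1.2.2 allows a switch for bosutinib failure up to 96 weeks after the last first dose. A switch at that limit puts the end at 96 + 48 = 144 weeks after the last first dose (ignoring the further 42 days allowed before asciminib starts). All 233 can then reach Weeks 108 to 144. The fall begins at Week 156, where f is again 84.2% (156 − 144 = 12 weeks).

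**Step 4, what is untouched.** The end date is never earlier than 96 weeks after the last first dose, so the planned end removes nobody at Weeks 24, 48 or 96. Duration of MMR is censored at the last on-treatment PCR, which handles the planned end properly. Rates by a visit and the cumulative incidence display cannot fall.

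**The case against.** The best reply is that planned completion is not discontinuation at all. Sections 4.3 and 6.1.5 contrast treatment to the end of the period with earlier discontinuation, and section 7.1.6 does not list the end of the period among its reasons. Time to treatment failure counts any discontinuation as an event yet provides for censoring, which would leave little to censor at the final treatment analysis if planned completers had discontinued. This stands as far as it goes: the text is ambiguous on the label, and the glossary entry is generic.

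It does not rescue the rates. Section 10.5.2 follows the Week 24 method, in which only patients in MMR at the visit respond. A planned completer with no later PCR fails that test whatever the stop is called. The imputation exception cannot help, because it needs a result after the visit and no PCR is scheduled after the planned end. Section 10.4.3 also marks discontinuation by an EOT visit, and Table 7-1 gives planned and early stops the same EOT column.

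A reader might infer three stronger things that the documents do not support:
- **That the same rule governs response after the switch.** It concerns randomised treatment, which switchers have already stopped. Section 10.6.1.1 plans to "estimate response rates (cytogenetic and molecular response) at all scheduled time points after switch" in the Switch Analysis Set and states no non-responder rule. Treatment also runs at least 48 weeks past the last switch, so the planned end removes no visit up to S-Week 48.
- **That every visit after Week 96 is certainly affected.** That depends on which limb sets the end date.
- **That a falling curve is planned.** No curve of these rates is specified.

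The impact is also limited. The rates are declared exploratory, and duration of MMR has its own sound analysis. Finally, the text at hand is marked as part 2 of 3. A rule for completers in a part not shown would settle the matter.

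**Conclusion.** Wrong as written, but only for the exploratory MMR rates at visits after Week 96. Applied as stated, the rule and the fixed FAS denominator turn planned completion into non-response, and the rates drop with enrolment date even when no response is lost.

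Under the 96-week limb, about 63% of the FAS (100% − 37%) would be non-responders at Week 144 for this reason alone, and a 23-point difference would read as 8.5. Under the longest switch limb the same fall is postponed to about Week 156, not removed. The sizes rest on the date, accrual and constant-rate assumptions listed in the working. The direction needs only staggered enrolment and a common end date.

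The primary and key secondary analyses, Week 48, the sample size, the power and the Kaplan-Meier duration of MMR are unaffected. The case for change is a modest one: misleading late descriptive rates, cheaply avoided.

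**What to change.** In section 10.5.2:
1. State that reaching the end of the study treatment period is not a discontinuation for the non-responder rule.
2. Report FAS rates at a visit only through the last visit every randomised patient could reach: Week 96, or later if the final end date allows.
3. For later visits, use as denominator only patients whose first dose was at least that many weeks before the end of the study treatment period, and show n. Patients in that denominator who stop early still count as non-responders.

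In section 10.6.1.1, where no rule is given, the same potential-follow-up denominator could be adopted for visits beyond S-Week 48.

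The cost is a few sentences and one derived variable. The downside is smaller denominators at late visits, made up of the earlier entrants. Under the 96-week limb, those able to reach Week 144 were nearly all randomised by 21-Nov-2018, before Amendment 3 (14-Dec-2018) relaxed the BCR-ABL1 entry threshold for intolerant patients. A footnote should say so.

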10.4.2 Statistical hypothesis, model, and method of analysis

The MMR rate at 24 weeks will be calculated based on the FAS and according to the Intention-To-Treat (ITT) principle. MMR rate and its 95% confidence interval based on the Pearson-Clopper method will be presented by treatment group. The confidence interval for the difference in MMR rate between treatment groups will be provided using the Wald method.

The null hypothesis is that there is no difference between the treatment groups with respect to MMR rate at 24 weeks. The Cochran-Mantel-Haenszel chi-square test, stratified by the randomization stratification factor, i.e. major cytogenetic response status (PCyR or CCyR vs. others) at screening, will be used to compare MMR rate between the two treatment groups, at the two-sided 5% level of significance. The Mantel-Haenszel estimate of the common risk difference and the corresponding 95% confidence interval will also be provided.

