10.5.1.1 Analysis for key secondary objectives

The null hypothesis is that there is no difference between the treatment groups with respect to MMR rate at 96 weeks. Formal statistical testing of the key secondary endpoint will be performed with $\alpha = 0.05$ (two-sided) only if the primary endpoint (i.e. MMR rate at 24 weeks) is significant by means of a gatekeeping procedure to control the overall alpha level. Otherwise, no statistical testing will be performed, and any analysis will be considered exploratory.

MMR rate at 96 weeks will be evaluated in a similar fashion to the primary analysis of MMR rate at 24 weeks. The rate and the associated 95% confidence interval based on the Pearson-Clopper method will be presented by treatment group. Confidence interval for the difference between treatment groups will be provided using the Wald method.

Statistical testing will be performed via CMH chi-square test stratified by the randomization strata. The Mantel-Haenszel estimate of the common risk difference and the corresponding 95% confidence interval will also be provided.

If the PCR evaluation at 96 weeks is missing, but a PCR evaluation both at 84 weeks and 108 weeks indicate MMR, the 96 week assessment is imputed as a “response”, assuming that MMR is maintained between 84 and 108 weeks. If PCR evaluations are performed at unscheduled visits closer to the Week 96 visit (before or after), these will be taken into account for the imputation.

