10.8 Sample size calculation

To test the null hypothesis that the response rate is equal in the two groups, based on two-sided 5% level of significance and with 90% power, 222 patients will be needed in total (i.e. 148 patients in the asciminib arm and 74 patients in the bosutinib arm based on 2:1 randomization allocation). This assumes that asciminib leads to a 20% improvement in the MMR rate at 24 weeks over bosutinib from 15% to 35% which corresponds to an odds ratio of 3.05.

The assumed bosutinib MMR rate of 15% at 24 weeks is based on previous trials evaluating bosutinib therapy ([Khoury 2012](#), [Gambacorti-Passerini 2014](#), [García-Gutiérrez 2015](#)).

No more than 66 patients (approximately 30% of the overall trial population) that are intolerant to their most recent TKI therapy with BCR-ABL1 < 1% will be recruited in order to ensure that the CML third line patient population is adequately represented.

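### With 2:1 allocation the planned Wald interval for differences in response rates has a lower limit that is too high, most clearly when few patients respond

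*Combined protocol and SAP*

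**What the plan says.** Three sections prescribe the Wald interval for the difference between arms.

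- Section 10.4.2 (MMR at 24 weeks, primary): "The confidence interval for the difference in MMR rate between treatment groups will be provided using the Wald method".
- Section 10.5.1.1 (MMR at 96 weeks, key secondary): "Confidence interval for the difference between treatment groups will be provided using the Wald method".
- Section 10.5.2 (MMR at and by the other scheduled visits, repeated for CCyR): "Confidence intervals for the differences in any response rates between treatment groups will be provided using the Wald method".

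Beside it, 10.5.2 plans a test, "Statistical testing will be performed via CMH chi-square tests stratified by the randomization strata", and a second interval, "The Mantel-Haenszel estimate of the common risk difference and the corresponding 95% confidence interval will also be provided". No variance is named for that second interval. For the primary endpoint the decision rule is the stratified CMH test, which "will be used to compare MMR rate between the two treatment groups, at the two-sided 5% level of significance". Rates within each arm get exact Pearson-Clopper intervals.

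Section 10.8 gives the arm sizes: "148 patients in the asciminib arm and 74 patients in the bosutinib arm based on 2:1 randomization allocation". Table 7-3 starts on-treatment PCR sampling at Week 4, followed by Weeks 8, 12, 16 and 24. Section 10.5.2 labels the non-key secondary endpoints exploratory.

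**The concern.** The Wald interval estimates each arm's variance from that arm's own observed rate. When the smaller arm happens to have few or no responders, its variance is estimated at or near zero. That same chance result moves the observed difference towards asciminib. The standard error is therefore too small exactly when the estimate favours asciminib, and the lower limit ends up too close to the estimate.

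Three things are at stake:

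- The error has a known direction, towards the sponsor's product.
- The interval can exclude zero when the chi-square test is not significant.
- With no responders in either arm, the interval has zero width (0.0 to 0.0) and suggests certainty.

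The plan takes care over the within-arm rates by using exact intervals, but gives the comparison, which matters more, a weaker method.

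**Working it through.** **Inputs.** Arm sizes 148 and 74, two-sided alpha 5% (2.5% per side), and planning rates 15% v 35% at Week 24 (Section 10.8); bosutinib 30% at Week 96 (Section 10.9). Discontinued patients count as non-responders, so the MMR denominators stay at the randomised numbers. The documents state no MMR rate before Week 24, so low rates are shown as a range.

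**The plan's own figure.** Pooled variance under the null, no continuity correction, allocation ratio 2. The pooled rate is (2×0.35 + 0.15)/3 = 0.2833. Then

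n(bosutinib) = [1.960·√(0.2833×0.7167×1.5) + 1.282·√(0.15×0.85 + 0.35×0.65/2)]² / 0.20² = 73.2.

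Rounded up this is 74, hence 148 + 74 = 222, as Section 10.8 states ("with 90% power, 222 patients will be needed in total"). The odds ratio is (0.35/0.65)/(0.15/0.85) = 3.05, also as stated.

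**One table by hand.** Take 5/148 v 0/74.

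- Difference: 3.38%.
- Wald SE = √(0.0338×0.9662/148 + 0) = 1.485%. The bosutinib arm contributes nothing.
- Wald interval: 3.38 ± 1.96×1.485 = 0.5% to 6.3%.
- Chi-square: expected asciminib responders 5×148/222 = 3.33; variance 148×74×5×217/(222²×221) = 1.091; z = 1.667/1.0445 = 1.60; p = 0.11.
- The SE under a common rate of 5/222 is √(0.0225×0.9775×(1/148 + 1/74)) = 2.11%, so the Wald SE is about 70% of it.
- Newcombe interval: −1.9% to 7.7%.

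Further tables: 7/148 v 0/74 gives Wald 1.3% to 8.2% with p = 0.058, and 10/148 v 1/74 gives 0.6% to 10.2% with p = 0.081.

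**Equal true rates.** All outcomes of Binomial(148, p) and Binomial(74, p) were enumerated. For each, the Wald limits were d ± 1.96·√(pₐ(1−pₐ)/148 + p_b(1−p_b)/74). Entries are percentages of trials; nominal is 2.5.

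| True rate | Wald excludes 0, favouring asciminib | Wald excludes 0, favouring bosutinib | Newcombe, asciminib / bosutinib side |
|---|---|---|---|
| 1% | 2.96 | 0.18 | 0.00 / 1.11 |
| 2% | 7.81 | 0.66 | 0.07 / 2.33 |
| 2.5% | 8.17 | 0.86 | 0.20 / 2.61 |
| 3% | 7.70 | 1.00 | 0.38 / 2.74 |
| 5% | 5.59 | 1.30 | 1.09 / 2.68 |
| 10% | 4.14 | 1.75 | 1.79 / 2.73 |
| 15% | 3.72 | 1.95 | 2.06 / 2.72 |
| 30% | 3.08 | 2.34 | 2.32 / 2.58 |

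The ratio to nominal is 7.81/2.5 = 3.1 at 2%, 3.3 at 2.5%, 3.1 at 3%, 2.2 at 5%, 1.7 at 10% and 1.5 at 15%. With 111:111 the asciminib-side figure is 2.1% at a 2% rate and 2.2% at 3%, so the excess comes from the unequal allocation.

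**Disagreement with the test.** Wald excludes zero in favour of asciminib while the chi-square is not significant in 7.6% of null trials at 2%, 6.8% at 3%, 3.9% at 5% and 1.5% at 15%. A two-stratum CMH simulation (1,000,000 trials per setting; assumed stratum shares of 30% and 50%; stratum rates equal or twofold apart) agrees to about 0.1 percentage point.

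**The second planned interval.** In that simulation the Mantel-Haenszel risk difference with the Greenland-Robins variance excluded zero in favour of asciminib about as often as Wald (7.8% at 2%).

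**Planned effects.** At 35% v 15% the Wald lower limit misses in 3.4% of trials and the upper in 2.1%, so coverage is 94.6%. At 53% v 30% (Week 96) the misses are 3.1% and 2.2%.

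**Zero width.** The chance of no responder in either arm is (1−p)²²²: 10.7% at a 1% rate and 1.1% at 2%.

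**Actual enrolment.** The Amendment 03-US.01 rationale reports 233 randomised, without the split. Assuming 155:78 or 157:76, the asciminib-side error is 7.4% to 8.3% at true rates of 2% to 3%.

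**The case against.** The strongest reply is that nothing formal hangs on this interval. The primary and key secondary conclusions rest on the CMH test, the 10.5.2 endpoints are exploratory, and at the planned rates Wald is close to nominal. All of that stands. It limits how much the point matters, but it does not make the stated method sound.

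A reader might infer that the threefold excess applies generally. The documents do not support that. It needs equal true rates of about 2% to 3%; it fades near 1% and shrinks steadily above 3%. The mechanism depends on bosutinib having zero or one responder, which has probability 56% at a 2% rate, 11% at 5% and 0.4% at 10%. Low rates at Weeks 4 and 8 are plausible: intolerant patients must enter above 0.1% IS, and bosutinib is planned at only 15% by Week 24. They remain an assumption.

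A reader might also expect the tables to show a Wald interval contradicting the CMH p-value beside it. For the exploratory visits that is uncertain. Section 10.5.2 says both that there will be no testing and that CMH tests will be done, and the Amendment 2 summary records that p-values were removed there.

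The Mantel-Haenszel interval is a fair point too, since readers would have two intervals. It helps only if its variance does not share the defect, and none is named.

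Finally, the alternatives are not symmetric. At a 2% rate a score-type interval errs 0.2% on the asciminib side and 3.6% on the bosutinib side; Newcombe errs 0.07% and 2.3%.

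The text available is one part of three, so a rule for sparse visits may stand elsewhere. As written, these sections contain none.

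**Conclusion.** The point holds, within limits. Under 148:74 allocation the Wald lower limit is too high throughout the range examined. The excess is about threefold at true rates of 2% to 3%, about twofold at 5%, and 1.5-fold at 15%. At the planned Week 24 effect it comes to a lower-side miss of 3.4% instead of 2.5%.

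The larger figures assume equal true rates and low early-visit response, neither of which the documents supply. The smaller figures need only the plan's own rates and arm sizes.

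It would be wrong to conclude that the trial's type I error is inflated or that the primary result could turn on this: the CMH test decides both formal hypotheses. This is a reporting weakness with a known direction. It should be corrected because the correction is cheap, not because a conclusion depends on it.

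**What to change.** In Sections 10.4.2, 10.5.1.1 and 10.5.2 (MMR and CCyR), replace the Wald interval for the difference by a Miettinen-Nurminen score interval stratified by the randomisation factor, or by a Newcombe interval. Keep the CMH test and the Mantel-Haenszel point estimate. For the Mantel-Haenszel interval, either drop it in favour of the stratified score interval or name a variance that does not share the defect. If it is kept with the Greenland-Robins variance, the problem stays in the tables.

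The cost is one sentence per section and a standard software option; no sample size, alpha or test changes. The reported lower limit becomes slightly less favourable. For 52/148 v 11/74, Wald gives 9.1% to 31.4% and Newcombe 8.1% to 30.5%. At very low rates the new interval will be conservative on the asciminib side, with some imbalance the other way.
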